3.5.2. Safety Laboratory Data

Safety laboratory testing will be performed at Screening, Days 1, 15, Weeks 12, 24, 36, 52, or ET visit. The details are listed in below table.

Hematology	Chemistry	Urinalysis	Other
Hemoglobin Hematocrit RBC count Platelet count WBC count Total neutrophils (Abs, %) Eosinophils (Abs,%) Monocytes (Abs,%) Basophils (Abs,%) Lymphocytes (Abs,%) PT	Urea and creatinine eGFR Glucose (fasting) Calcium Sodium Potassium Chloride Total CO ₂ (bicarbonate) AST, ALT Total and direct bilirubin Alkaline phosphatase Uric acid Albumin Total protein Magnesium Amylase Lipase Phosphorus hsCRP	Local dipstick: pH Glucose (qual) Protein (qual) Blood (qual) Ketones Nitrites Leukocyte esterase Laboratory: Microscopy and culture ^a	At screening: 
 • FSH^b • Pregnancy test (β-hCG)^c • Hepatitis B surface antigen and HbcAb. HBsAb and HBV DNA as reflex tests • Hepatitis C antibody and HCV RNA as reflex testHIV • HLA genotype and CeD serology (eg, HLA DQ2.5 and HLA DQ8 testing^d, tTG and DGP IgA/IgG^e)

- Only if UTI is suspected and urine dipstick is positive for nitrites or leukocyte esterase or both.
- For confirmation of postmenopausal status only.
- A serum pregnancy test is required at screening. Following screening, local urine testing will be standard for the protocol unless serum testing is required by local regulation or IRB/EC. Serum or urine β-hCG for female participants of childbearing potential.
- For re-screening, the HLA does not need to be repeated and CeD serology (the tTG and DGP antibody tests) should only be repeated if >3 months have elapsed from end assessment.
- For tTG, a result of <2 x ULN will be considered negative or weak positive. For DGP, a result of <30 U/mL will be considered negative or weak positive.

3.5.3. Vital Signs

Vital signs will be assessed at Screening, Days 1, 4, 7, 15, 28, Weeks 12, 24, 36, 52, or ET visit. On dosing days, orthostatic vital signs including SBP, DBP, and PR will be collected approximately 5 minutes pre-dose, and approximately 45 minutes, 2 hours, and then, every 2 hours until discharge, post dose.

4. ANALYSIS SETS

For purposes of analysis, the following analysis sets are defined for Part C:

Analysis Set	Description
Entered	All participants who sign the ICD.
Enrolled (Randomized or assigned to study intervention)	All entered participants who are randomized to study intervention in Part C.
Full analysis set (FAS)	All participants who are randomly assigned to study intervention and receive any portion of study intervention in Part C. Participants will be analyzed according to the intervention they are randomized.

Analysis Set	Description
Safety analysis set (SAS)	All participants who receive any portion of study intervention in Part C. Participants will be analyzed according to the intervention they actually received.
PK analysis set (PKAS)	All participants who receive any portion of study intervention and have at least one concentration value in Part C.

5. GENERAL METHODOLOGY AND CONVENTIONS

5.1. Hypotheses and Decision Rules

This protocol Part C is designed to establish the superiority of 3 doses of KAN-101 to PBO for the primary endpoint the change in IL-2 from pre-GC to post-GC at Day 15. The null hypothesis is that there is no difference between any dose of KAN-101 and PBO, and the alternative hypothesis is that there is a significant difference between at least one dose of KAN-101 and PBO. KAN-101 will be considered superior to PBO with respect to IL-2 response if the difference is statistically significant at the 2-sided 0.05 level. There is no adjustment for multiplicity.

5.2. General Methods

In general, count and percent will be presented for categorical variables. Number of observations, mean, standard deviation (SD), minimum (min), 1st, 2nd, 3rd quartiles, and maximum (max) will be presented for continuous variables. The coefficient of variation (CV, defined as SD/Mean; %CV=100*CV), geometric mean (GM), and geometric mean ratio (GMR) will also be included, where appropriate. Graphics may be used to present the data.

5.2.1. Analyses for Continuous Endpoints

For continuous endpoints in Part C, the change from baseline will be analyzed by timepoint using analysis of covariance (ANCOVA) model with treatment as a factor, baseline as a covariate. For endpoints without baseline, analysis of variance (ANOVA) model with treatment as a factor will be used for the analysis. Comparison of each dose group of KAN-101 to PBO (providing LSM of the treatments, LSM of the treatment difference, p-value and 95% CI) will be generated.

5.3. Methods to Manage Missing Data

Missing values will not be imputed for safety, efficacy and PK endpoints. If a PK concentration value is below Lower Limit of Quantification (LLOQ), that concentration value will be treated as 0 for all analysis. For IL-2, values below LLOQ will be treated as ½LLOQ.

6. ANALYSES AND SUMMARIES

Data will be summarized by treatment group. Efficacy analyses will be based on FAS, safety analyses will be based on the SAS, and PK analyses will be based on the PKAS. Demographics and baseline characteristics will be summarized for the SAS.

6.1. Primary Endpoint(s)

The primary endpoint is IL-2 change from pre-GC to post-GC on Day 15.

Raw data will be descriptively summarized by treatment group with number of observations, mean, SD, min, 1st, 2nd and 3rd quartiles, max, GM/GMR for FAS.

Log transformed IL-2 will be used in statistical analysis models (log transform each individual IL-2 value first, then calculate the change).

6.1.1. Main Analysis

- Estimand strategy: Hypothetical estimand, Estimand 2 ([Section 2.2.1](#)).
- Analysis set: FAS ([Section 4](#)).
- Variable: log transformed IL-2 change from pre-GC to post-GC on Day 15.
- Analysis method: ANCOVA model ([Section 5.2.1](#)).
- Intercurrent event: Prohibited medication, incomplete GC on Day 15, and discontinuation of study intervention. All data collected after any intercurrent events will be excluded. Missing values will not be imputed.
- The LSM change from pre-GC to post-GC (log transformed), LSM difference of the change between each KAN-101 group and PBO, 95% CI, and p-value will be presented. Exponentially transformed values for LSM, LSM difference, 95% CI will be presented as well.

Note: based on the population attribute of Estimand 2, participants who didn't meet the HLA inclusion criteria will be excluded from the analysis.

6.1.2. Sensitivity Analysis

- Estimand strategy: Treatment policy estimand, Estimand 3 ([Section 2.2.2](#))
- Analysis set: FAS ([Section 4](#))
- Variable: log transformed IL-2 change from pre-GC to post-GC on Day 15.
- Analysis method: ANCOVA in [Section 5.2.1](#)
- Intercurrent event: intercurrent events will not be considered for analysis. Missing values will not be imputed.
- The LSM change from pre-GC to post-GC (log transformed), LSM difference of the change between each KAN-101 group and PBO, 95% CI, and p-value will be

presented. Exponentially transformed values for LSM, LSM difference, 95% CI will be presented as well.

Note: based on the population attribute of Estimand 3, participants who didn't meet the HLA inclusion criteria will be excluded from the analysis.

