9.3.2.3. Sensitivity Analysis

For Part C, the sensitivity analysis will be based on treatment policy estimand using FAS. Further details will be given in the SAP.

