2.1. Modifications to the Analysis Plan Described in the Protocol

“Entered” analysis set is added to [Section 4](#), it is not in the protocol. The definition of “Enrolled” analysis set is different from that in the protocol.

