8. REFERENCES

1. Protocol KAN-101-02.

APPENDICES**Appendix 1. Summary of Efficacy Analyses**

Endpoint	Analysis Type	Population	Data Inclusion and Rules for Handling Intercurrent Events and Missing Data	Analysis Model
Change in IL-2 from pre-GC to post-GC at Day 15	Summary	FAS	Observed cases, no imputation for missing data.	N/A
	Main analysis	FAS	Data collected after intercurrent events will be excluded. Missing data will not be imputed.	ANCOVA with terms treatment, pre-GC IL-2 at Day 15
	Sensitivity/supplementary analysis	FAS	All data collected will be included regardless of intercurrent events. Missing data will not be imputed.	ANCOVA with terms treatment, pre-GC IL-2 at Day 15
CDS D (Each item and question of the CDS D as well as the CDS D Total Score, CDS D Gastrointestinal (GI) Score) change from baseline at each timepoint	Summary	FAS	Observed cases, no imputation for missing data.	N/A
CDS D 1-Day, 3-Day, 7-Day Nausea Score and Vomiting Frequency and change from baseline at each timepoint post-gluten challenge	Summary	FAS	Observed cases, no imputation for missing data.	N/A

Endpoint	Analysis Type	Population	Data Inclusion and Rules for Handling Intercurrent Events and Missing Data	Analysis Model
PGIS change from baseline at each timepoint	Summary	FAS	Observed cases, no imputation for missing data.	N/A
PGIC at each timepoint	Summary	FAS	Observed cases, no imputation for missing data.	N/A

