Week 24	Day 168	Day 127 – Day 210
Week 36	Day 252 pre-GC	Day 211 – Day 308
Week 52	Day 364	Day 309 – end of study

Table 7. Analysis for IL-2 and CDS (GC day at each time point)

Visit Label	Targeted Day	Analysis window for data sets
Day 15	Day 15	Day 14 -Day 16
Week 12	Day 84	Day 70 - Day 98
Week 24	Day 168	Day 154 – Day 182
Week 36	Day 252	Day 238 – Day 266

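### Both Part C primary analyses are labelled FAS but drop HLA failures and share a Day 14–16 IL-2 window, so comparing them cannot show what either restriction does

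*SAP*

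**What the plan says.** Protocol 9.3.2.2 bases the Part C main analysis on the FAS. Protocol 9.3.2.3 does the same for the check on it: "For Part C, the sensitivity analysis will be based on treatment policy estimand using FAS". SAP Part C section 4 defines the FAS as "All participants who are randomly assigned to study intervention and receive any portion of study intervention in Part C", with no genotype or timing condition; protocol 9.2 agrees.

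SAP 6.1.1 (main, hypothetical estimand) and 6.1.2 (sensitivity, treatment-policy estimand) both give FAS as the analysis set. Each then adds a note, resting on the population attribute of the estimand, that participants who did not "meet the HLA inclusion criteria will be excluded from the analysis". Appendix 1 has no such note; for the sensitivity run it says "All data collected will be included regardless of intercurrent events". The descriptive summary of the same endpoint in 6.1 is also on the FAS, again without the note.

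SAP 2.1 lists two departures from the protocol: a new Entered set, and an Enrolled definition whose "analysis set is different from that in the protocol". The HLA restriction is not listed.

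Table 7 in Appendix 2.1, which covers IL-2 and the symptom diary ("GC day at each time point"), maps Day 15 to Days 14–16. Its next window opens on Day 70.

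**The concern.** A sensitivity analysis tells us about a restriction only if it lifts that restriction. If both runs omit the same participants or the same samples, their agreement says nothing about the omission. The analysis that the protocol promised, treatment policy on everyone randomised and dosed, is then not delivered under that name. Tables of one endpoint, all labelled FAS, could also show different denominators without explanation.

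The two restrictions carry different risks. Genotype precedes randomisation. The day of the challenge comes after dosing, so a challenge delayed by an adverse event could be related to treatment. Losing such challenges from both runs would leave a possible arm-dependent loss unexamined.

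**Working it through.** **Step 1. What the sensitivity run lifts.** From SAP 6.1.1, 6.1.2, Appendix 1, Table 7 and protocol 7.1:

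| Restriction | Main analysis | Treatment-policy run | Tested by comparing them? |
|---|---|---|---|
| After prohibited medication | excluded | included | yes |
| Incomplete Day 15 challenge | excluded | included | yes |
| After discontinuing study intervention | excluded | included in principle | hardly: without 3 full doses there is no challenge and no IL-2 sample |
| HLA inclusion criterion not met | excluded | excluded | no |
| Day 15 challenge outside Days 14–16 | unassigned | unassigned | no |

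**Step 2. Does the stated reason match the rule?** The population attribute of both estimands is the full set of Part C inclusion and exclusion criteria. Only the HLA inclusion criterion is applied. HLA-DQ8 positivity, an exclusion criterion in protocol 5.2, is not.

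**Step 3. The window.** The SAP version history describes Table 7 as defining the IL-2 analysis window. A challenge on Day 17, for example, falls in no row, and SAP 5.3 imputes nothing. The tolerance is ±1 day at Day 15 but ±14 days at Week 12 (Days 70–98). PGIS and PGIC at the Day 15 visit use Days 8–21.

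**Step 4. The plan's own figure.** Protocol 9.5 assumes a difference of 2.37, an SD of 1.53, 26 per group and two-sided 5%. The standard error is 1.53 × √(2/26) = 0.424, and 2.37/0.424 = 5.59. Power by noncentral t on 50 df is 99.98% (normal approximation 99.99%), in line with the stated 99%.

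**Step 5. Size of the HLA restriction.** The documents give no counts, so k per arm is an assumed range. Suppose those k have no treatment effect, and let f = k/26. The FAS difference is 2.37 × (1 − f). FAS power uses an approximate SD of √(1.53² + f(1 − f) × 2.37²). Ratios assume natural logs.

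| k of 26 | f | Power if excluded | FAS difference | Ratio (10.7 at k = 0) | Power if kept |
|---|---|---|---|---|---|
| 1 | 3.8% | 99.97% | 2.28 | 9.8 | 99.9% |
| 2 | 7.7% | 99.95% | 2.19 | 8.9 | 99.7% |
| 3 | 11.5% | 99.9% | 2.10 | 8.1 | 99.1% |
| 5 | 19.2% | 99.8% | 1.91 | 6.8 | 96.5% |
| 8 | 30.8% | 99.5% | 1.64 | 5.2 | 87.0% |

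At k = 2 the restricted difference is 26/24 = 1.08 times the FAS difference.

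**Step 6. Size of a one-sided timing loss.** If k participants in one arm only are lost, and their log changes differ from those retained by x, that arm's mean moves by k × x/26. With k = 2 and x equal to one SD (both assumed), this is 2 × 1.53/26 = 0.118, or 5% of 2.37. The direction is unknown.

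**The case against.** Estimands 2 and 3 share a population attribute, so holding the population fixed while changing the intercurrent-event strategy is coherent. HLA has a pharmacological rationale: protocol 2.2.2 describes a peptide recognised by HLA-DQ2.5. The restriction is stated openly in both sections, protocol 9.3.2.3 leaves details to the SAP, and the opening of protocol section 9 allows the SAP to modify the plan. Protocol section 5 requires eligibility to be confirmed before randomisation and forbids waivers, so few people, perhaps none, are affected. On the window, no sentence says that off-window IL-2 is discarded, the general statement in Appendix 2.1 does not name IL-2, and the Part C schedule shows no tolerance for Day 15, so Days 14–16 is already wider than the schedule. PGIS recalls a week, whereas IL-2 is a single 4-hour sample, so the contrast between their windows is weak.

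Much of this stands. It removes any presumption of bias from the HLA restriction, and it argues for adding a run instead of redefining Estimand 3. It does not explain why a set narrower than the FAS carries that name, why SAP 2.1 is silent, or what happens to an off-window challenge for the primary endpoint.

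A reader might infer that the sensitivity run repeats all the main exclusions and is therefore worthless. Step 1 shows otherwise: the main rule, "All data collected after any intercurrent events will be excluded", is reversed for prohibited medication and incomplete challenge. A reader might also infer that the window removes people from the FAS. It does not; it maps samples to visits.

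**Conclusion.** The point holds as a matter of labelling, disclosure and what the sensitivity analysis can show. Neither primary analysis is run on the FAS as defined. The departure is undeclared, and the comparison of the two is uninformative about the HLA exclusion and the IL-2 window.

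The loss of off-window challenges is a strong inference from Table 7 and the absence of imputation; the SAP does not state it. Only timing has a plausible route to arm-dependent bias, and the documents report no delayed challenges. The HLA effect is about 8% on the log scale if 2 of 26 per arm had no treatment effect. That count is assumed, and the true effect may be nil. Power is not at issue: excluding even 8 of 26 per arm leaves about 99.5% at the planned effect and SD.

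The documents do not support reading this as a breach of the rule that major changes to the primary analysis need a protocol amendment, because they do not define major.

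**What to change.** - Add a separately labelled treatment-policy run on the FAS as section 4 defines it: no HLA exclusion, and the IL-2 pair from the nominal Day 15 challenge on whatever day it was performed. The present 6.1.2 analysis can stay beside it.
- Call the HLA-restricted set a modified FAS in 6.1.1, 6.1.2 and Appendix 1, and list it in SAP 2.1.
- State how the main analysis handles a Day 15 IL-2 pair outside Days 14–16.
- Report the numbers excluded by reason and arm.

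The cost is SAP wording and one more analysis, with no new data. The added estimate may be diluted by a few percent on the log scale.

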6.2. Secondary Endpoints

6.2.1. PK Concentration

PK concentration will be descriptively summarized by treatment group and nominal timepoints with number of observations, mean, SD, min, 1st, 2nd and 3rd quartiles, max for PKAS. Line plot will be provided by treatment group for mean (+/-SD) concentration-time profiles using linear and semi-log scale. Individual subject plasma concentration-time data will be plotted as well.

6.2.2. PK Parameters

PK parameters listed in [Section 3.2](#) (AUC_{inf} , AUC_{last} , C_{max} , T_{max} , and $t_{1/2}$) will be descriptively summarized by treatment group with number of observations, mean, SD, min, 1st, 2nd and 3rd quartiles, max, GM, and %CV for PKAS. No GM and %CV for T_{max} .

6.2.3. Incidence and Severity of TEAEs as Assessed by the CTCAE

See safety [Section 6.6.1](#).

6.3. Exploratory Endpoints

6.3.1. PK Parameters

Exploratory PK parameters will not be measured/reported due to study termination.

6.3.2. Incidence of Development of ADA During the Study

Participants positive for ADA (screening, confirmatory, specificity and titer) will be summarized by treatment group and timepoint with number and percent for SAS.

6.3.3. Change in circulating levels of IL-2 from pre-GC to and post-GC at Weeks 12, 24, and 36

These endpoints will not be measured/reported due to study termination.

6.3.4. Change in Circulating Levels of IL-2 Response pre- and post-GC in Peripheral Blood from GC at Day 15 to GC at Weeks 12, 24, and 36

These endpoints will not be measured/reported due to study termination.

6.3.5. Change in circulating levels of various biomarkers from pre-dose to post-dose on Day 1, 4, and 7

These endpoints will not be measured/reported due to study termination.

6.3.6. PROs

6.3.6.1. CSDS

Weekly scores for each item and question of the CSDS as well as the CSDS Total Score, CSDS Gastrointestinal (GI) Score (see [Section 3.3](#) and [Appendix 2.2](#)) and change from baseline will be descriptively summarized with number of observations, mean, SD, min, 1st, 2nd and 3rd quartiles, max for each treatment group by timepoint. The change from baseline will be analyzed using ANCOVA models in [Section 5.2.1](#) by timepoint. LSM of the treatments, LSM of the treatment difference with PBO, p-value and 95% CI will be generated. The summary and analysis will be performed for weekly average at weeks 3, 12, 24, 36, as well as for daily assessment at GC Day 15, and Weeks 12, 24, 36 GC. The weekly average score is the weekly sum score divided by the number of days with non-missing in that week. If daily scores are missing for more than half of total days in a specific week or the score on GC day is missing, the average score is set as missing for that week.

The change from baseline in CSDS Nausea score and vomiting frequency for Day 15, Week 12, Week 24 and Week 36 GC will be evaluated as a 1-day, 3-day and 7-day score, summarized as stated above, and analyzed within each KAN treatment, and combined, evaluating the paired difference from baseline using the Wilcoxon Signed-rank test. The Mann-Whitney U test (Wilcoxon Rank Sum test) will be used to test the difference in the change from baseline for placebo vs each of KAN group.

Line plots by treatment group will be provided for mean (\pm SD).

Due to study termination, only descriptive summaries will be provided for data up to Week 12.

6.3.6.2. PGIS

PGIS and change from baseline will be descriptively summarized with number of observations, mean, SD, min, 1st, 2nd and 3rd quartiles, max for each treatment group by timepoint. The change from baseline will be analyzed using ANCOVA models in [Section 5.2.1](#) by timepoint. LSM of the treatments, LSM of the treatment difference with PBO, p-value and 95% CI will be generated.

Due to study termination, only descriptive summaries will be provided for data up to Week 12.

6.3.6.3. PGIC

PGIC will be descriptively summarized with number of observations, mean, SD, min, 1st, 2nd and 3rd quartiles, max for each treatment group by timepoint. PGIC will be analyzed using ANOVA models in [Section 5.2.1](#) by timepoint. LSM of the treatments, LSM of the treatment difference with PBO, p-value and 95% CI will be generated.

Due to study termination, only descriptive summaries will be provided for data up to Week 12.

6.3.7. Biopsy Substudy

Biopsy substudy endpoints will not be measured/reported due to study termination.

6.4. Subset Analyses

N/A

6.5. Baseline and Other Summaries and Analyses

6.5.1. Baseline Summaries

Demographic and baseline characteristics listed in [Section 3.4](#) will be summarized according to Sponsor's reporting standards for SAS.

6.5.2. Study Conduct and Subject Disposition

Participants evaluation, disposition, discontinuation will be summarized for SAS according to Sponsor's reporting standards.

6.5.3. Study Treatment Exposure

The exposure to study drug will be summarized by treatment group for number of doses of study intervention applied for SAS.

6.5.4. Gluten Challenge

GC will be summarized by number and percentage of participants completed GC at each GC scheduled timepoint for SAS.

6.5.5. Concomitant Medications and Non-Drug Treatments

Prior drug and non-drug treatment, concomitant drug and non-drug treatment will be summarized according to Sponsor's reporting standards.

6.6. Safety Summaries and Analyses

Safety analyses will be based on the SAS.

All clinical TEAEs, SAEs, withdrawal due to AEs, vital signs and safety laboratory data will be reviewed on an ongoing basis during the study to evaluate the safety of participants.

Safety data will be presented in tabular and/or graphical format and summarized descriptively, where appropriate. All safety endpoints will be listed and summarized in accordance with Sponsor's Standards. Categorical outcomes (eg, AEs) will be summarized by participant counts and percentage. Continuous outcome will be summarized using N, mean, median, SD, min, max. Participant listings will be produced for these safety endpoints accordingly.

6.6.1. Adverse Events

Adverse events will be summarized for SAS according to Sponsor's reporting standards for

- TEAEs
- Serious AEs (SAEs)

TEAEs will be summarized by the number of participants reporting any TEAE, system organ class (SOC), preferred term (PT), severity, relationship to investigational product.

CTCAE is used to grade the severity of AEs. TEAEs related to GC and infusion-related reactions (IRR) will also be summarized separately.

SAEs will be summarized by SOC and PT, and individual SAEs will be listed by participant.

A list of subjects who prematurely discontinue from the study due to an AE will be provided as well.

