For Part A, the primary endpoint is incidence and severity of TEAEs as assessed by CTCAE.

For Part B, the primary endpoint is change in magnitude of IL-2 response pre- and post-GC in peripheral blood from baseline screening to Day 15.

For Part C, the primary endpoint is the change in IL-2 from pre-GC to post-GC on Day 15 in participants treated with KAN-101 versus PBO.

Main Analytical Approach:

- **For Part A**, number and percent of participants with TEAEs will be summarized by cohort, SOC, PT, and severity.
- **For Part B**, the primary endpoint will be descriptively summarized by treatment using Estimand 1 for FAS. There is no statistical hypothesis testing.
- **For Part C**, change in IL-2 from pre-GC to post-GC on Day 15 will be analyzed using ANOVA model.
 - The main analysis of the primary endpoint will be based on Estimand 2 using FAS. The LSM difference of the change from pre-GC to post-GC on Day 15 (log transformed) between each KAN-101 group and PBO will be provided; prohibited medications, incomplete GC at Day 15, and discontinuation of study intervention are intercurrent events. All data collected after any intercurrent events will be excluded.
 - All statistical tests will be 2-tailed at a $\alpha = 0.05$.

Secondary Endpoint Analysis

For Part A, PK concentration and PK parameters will be descriptively summarized by treatment group.

[figure not shown]
For Part B and Part C, number and percent of participants with TEAEs will be summarized by treatment, SOC, PT, and severity. PK concentration and PK parameters will be descriptively summarized by treatment group. Number of TEAEs (all-causality and treatment-related) and percent of participants with TEAEs will also be summarized by treatment period, treatment, SOC, PT, and severity.

Ethical Considerations:

The overall potential benefit/risk of KAN-101 is considered favorable. Taking into account the measures to minimize risk to study participants, the potential risks identified in association with KAN-101 are justified by the anticipated benefits that may be afforded to participants with CeD.

[figure not shown]

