9. STATISTICAL CONSIDERATIONS

Detailed methodology for summary and statistical analyses of the data collected in this study is outlined here and further detailed in the SAP, which will be maintained by the sponsor. The SAP may modify what is outlined in the protocol where appropriate; however, any major modifications of the primary endpoint definitions or their analyses will also be reflected in a protocol amendment.

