9.3.3. Secondary Endpoints Analysis

For Part A, PK concentration and PK parameters will be descriptively summarized by treatment group. The PK parameters to be assessed, their definition, and method of determination are detailed in [Section 9.3.5](#). Actual PK sampling times will be used in the derivation of PK parameters.

For Part B and Part C,

- Number and percent of participants with TEAEs will be summarized by treatment, SOC, PT, and severity. Number of TEAEs (all-causality and treatment-related) and percent of participants with TEAEs will also be summarized by treatment period, treatment, SOC, PT, and severity.
- PK concentration and PK parameters will be descriptively summarized by treatment group.

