6.6.1. Adverse Events

Adverse events will be summarized for SAS according to Sponsor's reporting standards for

- TEAEs
- Serious AEs (SAEs)

TEAEs will be summarized by the number of participants reporting any TEAE, system organ class (SOC), preferred term (PT), severity, relationship to investigational product.

CTCAE is used to grade the severity of AEs. TEAEs related to GC and infusion-related reactions (IRR) will also be summarized separately.

SAEs will be summarized by SOC and PT, and individual SAEs will be listed by participant.

A list of subjects who prematurely discontinue from the study due to an AE will be provided as well.

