3.5.1. Adverse Events

Incidence and severity of TEAEs is the Secondary endpoint of Part C.

An adverse event (AE) is considered TEAE to a given treatment if the event start date is on or after the treatment period start date and before end of study.

The CTCAE (V5.0) displays Grades 1 through Grade 5 with unique clinical descriptions of severity for each AE based on below general guideline:

- **Grade 1:** Mild; asymptomatic or mild symptoms; clinical or diagnostic observations only; intervention not indicated.
- **Grade 2:** Moderate; minimal, local or noninvasive intervention indicated; limiting age appropriate instrumental activities of daily living (ADL).
- **Grade 3:** Severe or medically significant but not immediately life-threatening; hospitalization or prolongation of hospitalization indicated; disabling; limiting selfcare ADL.
- **Grade 4:** Life-threatening consequences; urgent intervention indicated.
- **Grade 5:** Death related to AE.

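### The Part B and Part C SAPs drop, without declaring it, the by-period adverse event summary that the protocol promises

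*SAP*

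**What the plan says.** Incidence and severity of TEAEs is a secondary endpoint of Parts B and C. Protocol 9.3.3 first plans tables by treatment, SOC, PT and severity, and then adds that "Number of TEAEs (all-causality and treatment-related) and percent of participants with TEAEs will also be summarized by treatment period". The synopsis repeats the commitment: "percent of participants with TEAEs will also be summarized by treatment period, treatment, SOC, PT, and severity".

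SAP B 6.6.1 and SAP C 6.6.1 use identical text: "TEAEs will be summarized by the number of participants reporting any TEAE, system organ class (SOC), preferred term (PT), severity, relationship to investigational product". Both add that "TEAEs related to GC and infusion-related reactions (IRR) will also be summarized separately". Section 6.6 of each specifies participant counts and percentages for categorical outcomes, plus participant listings. Neither plans a table by period or a count of events.

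Both SAPs count an event as a TEAE if the "event start date is on or after the treatment period start date and before end of study" (3.5.1). Protocol 8.2.1 has symptoms associated with a GC recorded as adverse events.

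Protocol section 9 allows for changes: "The SAP may modify what is outlined in the protocol where appropriate". Section 2.1 of each SAP is where departures are listed. It names only the added Entered set and an Enrolled definition for which the "analysis set is different from that in the protocol". Table 1 (version history) of SAP B and of SAP C does not mention the adverse event tables.

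**The concern.** The SAPs leave out part of a promised secondary-endpoint analysis and do not say so. The missing part is the one that separates events by timing, and timing matters in this trial for three reasons.

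- **Overlapping symptoms.** Protocol 2.3.1 lists the same ten symptoms as expected for the study drug and for the GC. A pooled table cannot tell them apart.
- **Possibly opposing effects.** Protocol 2.2.3 reports that in the first-in-human study more participants had GI events on drug than on placebo, while one dose level lowered median IL-2 after GC. If the drug raises dosing-phase symptoms and lowers GC symptoms, pooling could hide or reverse a difference between arms.
- **The safety question itself.** Protocol 4.2 says Part B was closed because the screening GC may have sensitized participants and so worsened events after dosing. It says Part C added assessments to learn about the period just after dosing.

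Under the SAPs as written, no specified summary table shows adverse events in that period by arm on timing alone. The reader must use investigator attribution or go through listings.

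**Working it through.** **1. The texts side by side**

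| Element | Protocol 9.3.3 and synopsis, Parts B and C | SAP B and C 6.6.1 | SAP A 6.1 |
|---|---|---|---|
| Participants with TEAEs by SOC, PT, severity | yes | yes | yes |
| Product-related TEAEs | yes, by period | yes, overall only | yes |
| Split by period | yes | no | yes: overall, and Day 1 to before the Day 15 GC |
| Number of events | yes | no | not promised for Part A |
| Departure declared in 2.1 or version history | – | no | – |

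The Part A split matches Part A's dose-escalation safety review period (protocol 4.1.1.1.2). It shows that a cut is workable; it is not a rule for Parts B and C.

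**2. Number of challenges in the TEAE window**

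The GC visits after dosing are Day 15 and Weeks 12, 24 and 36, so 4 in each part. The Part B run-in GC makes 5 in total but comes before treatment starts. This reproduces protocol 2.3.1: up to four in Part C and up to five in Part B.

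**3. Share of the TEAE window**

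Planned follow-up runs to Day 364.

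- Days 1-7: 7/364 = 1.9%.
- Days 1-14, before the first post-dose GC: 14/364 = 3.8%.
- Day 15 onward: 350/364 = 96.2%, with all four challenges.
- If termination ended follow-up at Day 84 or Day 28 (assumption), Days 1-14 are 14/84 = 16.7% or 14/28 = 50%.

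Time share is not event share.

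**4. Illustration for the any-TEAE row (all rates assumed)**

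Let p be the chance of a dosing-phase event and g the chance of reacting to at least one GC, taken as independent. Then any-TEAE risk = 1 - (1-p)(1-g). Take p = 0.50 on KAN-101 and 0.20 on placebo: a difference of 30 points, or 7.8 of 26 participants.

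| g, KAN-101 / placebo | Any TEAE, KAN-101 / placebo | Difference | Of 26 |
|---|---|---|---|
| 0.3 / 0.3 | 0.65 / 0.44 | +21 points | 5.5 |
| 0.5 / 0.5 | 0.75 / 0.60 | +15 | 3.9 |
| 0.8 / 0.8 | 0.90 / 0.84 | +6 | 1.6 |
| 0.3 / 0.5 | 0.65 / 0.60 | +5 | 1.3 |
| 0.5 / 0.8 | 0.75 / 0.84 | -9 | -2.3 |

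With equal g the pooled difference is (p1 - p0)(1 - g). The fraction kept, 1 - g, does not depend on the chosen p: 70%, 50% and 20% in the first three rows. As a second case, take p = 0.60 v 0.20 (40 points) and a 20% chance of symptoms at each of four challenges in both arms. The difference is then 40 × 0.8^4 = 16.4 points; after one challenge it is 40 × 0.8 = 32.

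**5. The tables that are planned (rates assumed)**

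- *Product-related table.* Suppose a fraction m of GC reactors is coded as product-related, so that m × g replaces g. With g = 0.8 / 0.8, m = 0.10 or 0.25 leaves 30 × 0.92 = 27.6 or 30 × 0.80 = 24.0 points. With g = 0.5 / 0.8, m = 0.10 gives 0.525 - 0.264 = 26.1 points, and m = 0.25 gives 0.5625 - 0.36 = 20.3 points.
- *Grade 3+ row.* For a 20-point dosing-phase difference and an equal GC Grade 3+ rate g3 of 0.05, 0.10 or 0.20, 20 × (1 - g3) = 19, 18 or 16 points.

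**6. Granularity**

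One participant is 1/26 = 3.8 points in Part C and 1/4 = 25 points in Part B.

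**The case against.** The strongest reply is that not restating a table is not the same as removing it. SAP B and C 6.6.1 refer to the sponsor's reporting standards, which may produce a period table, and the protocol sentence was never withdrawn. That possibility stands, but neither SAP says so. SAP A cites the same standards and still writes its time split out.

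Next, the planned tables cover much of the ground. TEAEs are split by relatedness, and GC-related events and infusion-related reactions get their own tables. Protocol 8.2.1 treats GC-associated events as separate from drug-related ones. Attribution must weigh timing (protocol 10.3.3), the last dose on Day 7 is eight days before the Day 15 GC, and the reported half-life is 3.74 to 36.8 minutes. Much of this stands, and step 5 bears it out. However, the relatedness and GC tables still rest on judgment between identical symptom lists. The infusion-reaction examples in protocol Appendix 9, which are not exhaustive, include no GI-specific symptom. The protocol also promised the period split for all-causality and for related events, so attribution was not meant to replace timing.

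The rates are assumed, and independence can be questioned because participants who withdraw without three full doses get no GC (protocol 7.1). Both points are fair. Anyone with a dosing-phase event is already in the any-TEAE row, so only GC reactions among the others affect it.

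Finally, the tables are descriptive, listings exist, the DSMB reviews unblinded data, and termination may mean fewer challenges. These points limit the stakes, chiefly in Part B. They weigh less in Part C, where listings would cover about 104 participants and the Day 15 GC remains in the window.

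**Conclusion.** The point holds. The documents alone show an undeclared departure from a promised secondary-endpoint summary: no period split and no event counts in SAP B or SAP C. The protocol permits such a change; the defect is that it is neither stated nor justified.

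The practical loss is mainly in the Part C any-TEAE, SOC, PT and lower-grade rows. Its true size cannot be derived from the documents. On the assumed rates, a 30-point dosing-phase difference could appear as anything from 21 points to a reversal of 9 points. The product-related table keeps 20.3 to 27.6 of 30 points and a Grade 3+ row 16 to 19 of 20, so the safety signal would not vanish from the report. These figures rest on assumed event and miscoding rates and on independence. The loss in Part B is small. This should be corrected, but it does not undermine the primary analysis.

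**What to change.** - **SAP C 6.6.1.** Add the promised tables by period and treatment group: number of events (all-causality and treatment-related) and percent of participants, by SOC, PT and severity.
- **Define the periods**, because the protocol does not do so for tabulation. One suitable choice is first infusion to before the Day 15 GC, then Day 15 GC onward, plus overall. State how this relates to the protocol's Day 1 to Day 7 treatment period.
- **Day 15 rule.** The TEAE definition uses start date, so say how events on Day 15 are assigned if onset time was not collected.
- **SAP B 6.6.1 (lower priority).** Do the same, or add a period column to the adverse event listing.
- **If the split is dropped on purpose**, declare and justify that in section 2.1 of each SAP.

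The cost is one SAP paragraph and a few filtered repeat tables for Part C, and perhaps one listing column for Part B. A date filter needs no new data; splitting Day 15 itself needs onset times or the stated rule.
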